7.6.1 Adverse Events

Summary:

- Overall summary of any AEs by worst CTC grade (Grade 1, 2, 3, 4, 3-4, 5, unknown) presented by SOC/PT
- Overall summary of treatment-related AEs by worst CTC grade (Grade 1, 2, 3, 4, 3-4, 5, unknown) presented by SOC/PT

Listing:

All recorded adverse events occurring in the pre-treatment, on-treatment, and post-treatment period will be listed.

7.6.2 Deaths

Summary:

All deaths during the study within 150 days after the last dose of study drug will be summarized for cause of deaths by treatment.

Listing:

All recorded deaths during the study (after a subject is enrolled and has signed the informed consent), including post-treatment follow-up period, and deaths that resulted from a process that began during the study, will be listed.

7.6.3 Serious Adverse Events

Summary:

• Overall summary of SAEs by worst CTC grade (Grade 1, 2, 3, 4, 3-4, 5, unknown) presented by SOC/PT

• Overall summary of treatment-related SAEs by worst CTC grade (Grade 1, 2, 3, 4, 3-4, 5, unknown) presented by SOC/PT

Listing:

A by-subject SAE listing will be provided for the All Enrolled Subjects.

7.6.4 Adverse Events Leading to Discontinuation of Study Therapy

Adverse events leading to study drug discontinuation are AEs with action taken = "Drug was discontinued".

Summary:

- Overall summary of AEs leading to discontinuation by worst CTC grade (Grade 1, 2, 3, 4, 3-4, 5, unknown) presented by SOC/PT
- Overall summary of treatment-related AEs leading to discontinuation by worst CTC grade (Grade 1, 2, 3, 4, 3-4, 5, unknown) presented by SOC/PT

Listing:

By-subject AEs leading to discontinuation listing will be provided.

7.6.5 Select Adverse Events

Summary of Select Adverse Events of Hypersensitivity/Infusion Reaction will be provided by ADA Status (Positive, Negative) for all Immunogenicity Subjects by treatment group and overall.

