As of 30-Aug-2016, 159 subjects were treated with the lirilumab plus nivolumab combination in Study CA223001. Nivolumab was administered at 3 mg/kg Q2W and lirilumab was administered Q4W at doses ranging from 0.1 mg/kg to 3 mg/kg. Most of the 159 treated subjects were treated at the nivolumab 3 mg/kg + lirilumab 3 mg/kg Dose Level. TRAEs and Grade 3 to 4 TRAEs were reported in 72% (114/159) and 15% (24/159) of subjects, respectively. Discontinuations due to TRAEs occurred in 8% (12/159) of subjects. The rates of AEs of the combination of lirilumab and nivolumab are consistent to what has been reported with nivolumab monotherapy with the exception of infusion related reactions which were higher in the combination. These infusion reactions were Grade 1 and 2 events only, which occurred mainly with the first infusion and did not lead to discontinuation.

As of 15-Jul-2016, 22 subjects were treated with the lirilumab plus ipilimumab combination in Study CA223002. Ipilimumab was administered at 3 mg/kg and lirilumab was administered at doses ranging from 0.1 to 3 mg/kg. Subjects received lirilumab in combination with ipilimumab Q3W for a total of 4 doses (induction), and then Q12W for an additional 4 doses starting at Week 24 (maintenance). Three subjects were administered lirilumab 0.1 mg/kg + ipilimumab 3 mg/kg, 8 with lirilumab 0.3 mg/kg + ipilimumab 3 mg/kg, 6 with lirilumab 1 mg/kg + ipilimumab 3 mg/kg, and 5 with lirilumab 3 mg/kg + ipilimumab 3 mg/kg. At the second dose level (lirilumab 0.3 mg/kg + ipilimumab 3 mg/kg), 1 subject reported iridocyclitis during the DLT period. This was a Grade 2 event that did not improve to Grade 1 within 2 weeks despite treatment with topical and intraocular injection of steroids, resulting in a DLT. The second cohort (lirilumab 0.3 mg/kg + ipilimumab 3 mg/kg) was thus expanded to 6 evaluable subjects. In the third cohort (lirilumab 1 mg/kg + ipilimumab 3 mg/kg), 1 subject reported a DLT of Grade 3 rash. This cohort was thus expanded to 6 evaluable subjects, and no further DLT occurred in these subjects. In the fourth cohort (lirilumab 3 mg/kg + ipilimumab 3 mg/kg), 5 subjects were enrolled; 2 subjects completed DLT evaluation period while 3 subjects progressed during DLT period and withdrew from the study. The study was terminated on 08-Dec-2014, and last patient last visit was occurred on 21-Apr-2015. This termination was due to strategic reasons and not due to any safety concerns.

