8.4.8 Other Analyses

A listing will be provided of all available immunogenicity data. Additionally, a listing of immunogenicity data from those subjects with at least 1 positive ADA at any timepoint will be provided by treatment for each analyte. The number (%) of subjects with the following anti-drug responses will be reported for each analyte if applicable, by dose, and overall: Baseline ADA

Positive, ADA Positive (Persistent Positive, Only the Last Sample Positive), ADA Positive with Neutralizing Positive, and ADA Negative.

To examine the potential relationship between immunogenicity and safety, the frequency and type of AEs of special interest may be examined by overall immunogenicity status. Associations between trough concentrations of lirilumab (or nivolumab or ipilimumab) and corresponding ADA assessments may be explored.

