4.2.4 Immunogenicity

Endpoints for the study are incidence rates of persistent positive ADA as well as neutralizing positive ADA from initiation of each drug treatment and up to and including the follow-up period of the last study drug dosing. Based on recommendation from BMS Immunogenicity Council, Harmonization of Clinical Immunogenicity Reporting by an Initiative of the Therapeutic Protein Immunogenicity Focus Group of the American Association Pharmaceutical Scientists, and the FDA Guidance for Industry Immunogenicity Assessment for Therapeutic Protein Products, the following definitions will be applied.

ADA Status of a Sample:

- Baseline ADA-Positive Sample: ADA is detected in the last sample before initiation of treatment
- ADA-Positive Sample: After initiation of treatment, (1) an ADA-positive sample in a subject who is baseline ADA-negative, or (2) an ADA-positive sample with ADA titer to be significantly increased (at least 9-fold for lirilumab and at least 4-fold for nivolumab) relative to baseline according to the corresponding analyte assay.
- ADA-Negative Sample: After initiation of treatment, ADA not-positive sample relative to baseline

ADA Status of a Subject:

- Baseline ADA-Positive Subject: A subject with baseline ADA-positive sample
- ADA-Positive Subject: A subject with at least one ADA-positive sample relative to baseline at any time after initiation of treatment during the defined observation time period, such as:
 - Persistent Positive: ADA-positive sample at 2 or more sequential timepoints, where there
 is an adequate elapse of time between the first and last ADA-positive samples (16 weeks
 for both BMS-986015 and nivolumab)
 - Only the Last Sample Positive: Not persistent but ADA-positive sample in the last sampling timepoint
 - Other Positive: Not persistent but some ADA-positive samples with the last sample being negative
 - Neutralizing Positive: At least one ADA-positive sample with neutralizing antibodies detected.

• ADA-Negative Subject: A subject with no ADA-positive sample after the initiation of treatment

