6.3 Populations for Analyses

- All Enrolled Subjects: All subjects who signed an informed consent and were registered into IRT;
- All Treated Subjects: All subjects who have received at least one dose of study medication;
- Response-Evaluable Subjects: All treated participants with measurable disease at baseline and one of the following: 1) at least one post-baseline tumor assessment, 2) clinical progression, or 3) death
- All Randomized Subjects: all subjects who were randomized in Part 3. This population will be used for listing of randomization schedule for Part 3 only.
- Lirilumab PK: all subjects who receive at least 1 dose of lirilumab and have adequate serum concentration data for lirilumab PK.
- Nivolumab PK: all subjects who receive at least 1 dose of nivolumab and have adequate nivolumab PK.
- Lirilumab Immunogenicity: all subjects who receive at least 1 dose of lirilumab and have at least 1 ADA sample available.
- Nivolumab Immunogenicity: all subjects who receive at least 1 dose of nivolumab and have at least 1 ADA sample available.
- Biomarker: all treated subjects who have biomarker data available.

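### SAP 7.6.5 tabulates infusion reactions by ever/never ADA status with no timing rule, so it mixes reactions before and after ADA and confounds ADA with time on treatment

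*SAP*

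**What the plan says.** SAP 7.6.5 plans one table: "Summary of Select Adverse Events of Hypersensitivity/Infusion Reaction will be provided by ADA Status (Positive, Negative) for all Immunogenicity Subjects", by treatment group and overall. It gives no rule on when a reaction must occur relative to ADA.

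SAP 4.2.4 fixes the two groups. Positive is "ADA-Positive Subject: A subject with at least one ADA-positive sample relative to baseline at any time after initiation of treatment". Negative is "A subject with no ADA-positive sample after the initiation of treatment". Baseline positivity, where "ADA is detected in the last sample before initiation of treatment", is a separate category that the 7.6.5 table does not use. SAP 6.3 admits to the lirilumab immunogenicity population "all subjects who receive at least 1 dose of lirilumab and have at least 1 ADA sample available", with a matching rule for nivolumab, so a baseline sample alone is enough.

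SAP 7.6 counts adverse events from the first dose to 150 days after the last, with summary tables for Parts 1 and 2 combined. Protocol 8.4.8 gives the aim: "To examine the potential relationship between immunogenicity and safety", using overall immunogenicity status.

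On timing, Protocol 1.4.13.3 describes the infusion reactions as Grade 1 and 2 events "which occurred mainly with the first infusion and did not lead to discontinuation". Protocol 1.4.17.2 says much the same. Protocol 8.3.2.1 lists ADA measurement at Weeks 1, 3, 5, 13, 17, 33, 49, 65 and 81, at end of treatment and at follow-up. The synopsis says samples are taken before dosing.

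**The concern.** A subject's column in this table is decided by samples drawn after most of the counted events have happened. The Day 1 sample precedes the first infusion and serves as baseline. A reaction at that infusion cannot result from ADA that treatment later induces, yet it is counted under the subject's eventual status.

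Time on treatment then confounds what remains. A subject who stays longer has more ADA samples, hence more chances to be called positive, and more infusions at which to react. Two default rules add to this: a subject with only a baseline sample counts as negative, and so does a baseline-positive subject without the required titer rise. Baseline ADA is the only ADA status that precedes a first-infusion reaction.

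At stake is what the study report can say about ADA and infusion reactions. A flat table could hide a real effect, and an excess could be an artefact of exposure.

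**Working it through.** **Base rate.** Protocol Section 1 (clinical experience with the combination) reports infusion-related reactions in 43 of 322 subjects: 43/322 = 0.1335, the stated 13.4%. Protocol 1.4.17.2 gives 18%.

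**Order of events.** In Tables 5.7.3.3-1, -2 and -4 the next ADA sample after Day 1 is Day 15. The note in Table 5.1.1-2 also lists Days 2 and 8, but both still follow the first infusion. On either reading, a first-infusion reaction precedes every post-baseline ADA sample.

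**Dilution of a true effect.** Assume a share f of reactions falls at the first infusion regardless of later ADA, 10% of subjects are ever ADA-positive, and later reactions are r times as frequent in them. Treat first-infusion and later reactors as separate groups, so that risks add. Per unit of overall risk, the later risk in ADA-negative subjects is

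l = (1 − f)/(0.9 + 0.1r)

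and the crude ratio is

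(f + r·l)/(f + l).

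The overall rate cancels, so 13.4% or 18% makes no difference. Example with f = 0.8, r = 5: l = 0.2/1.4 = 0.143, and the ratio is (0.8 + 0.714)/(0.8 + 0.143) = 1.61.

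| Share at first infusion | True r = 3 | True r = 5 |
|---|---|---|
| 70% | 1.53 | 1.94 |
| 80% | 1.34 | 1.61 |
| 90% | 1.17 | 1.29 |

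The model gives ever-positive subjects the raised risk at all later infusions. If the risk rose only once ADA appeared, the crude ratio would be closer to 1.

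**Spurious excess with no effect.** A simulation of 1,000,000 subjects per scenario set the ADA effect to nil. All inputs are assumed except the on-treatment ADA schedule and the two-weekly nivolumab infusions: exponential time on treatment with median 12 weeks, exponential time to ADA with mean 150 weeks (7.6 to 7.9% found positive), and a reaction risk per later infusion of 0.4% or 0.8%. First-infusion risk was 0.15 × 0.75 = 11.25% or 0.15 × 0.60 = 9%.

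| Share at first infusion | Early stopping among first-infusion reactors | ADA-positive | ADA-negative | Ratio |
|---|---|---|---|---|
| about 80% | none | 17.1% | 13.8% | 1.24 |
| about 62% | none | 20.3% | 14.1% | 1.44 |
| about 80% | 30% before Day 15 | 14.2% | 14.1% | 1.01 |
| about 62% | 30% before Day 15 | 18.0% | 14.3% | 1.26 |

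The stopping rows are a stress case, since Protocol 1.4.13.3 says the reactions did not lead to discontinuation. End-of-treatment and follow-up ADA samples were not modelled. Including them would probably weaken the link between exposure and detection.

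**The case against.** The table is descriptive, with no test and no decision attached, and Protocol 8.4.8 says only that such an examination may be made. A reader might infer that it cannot show an ADA effect at all. That goes too far: later reactions are in the table and carry information, but are not separated out.

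A reader might also infer that this is the only planned analysis of immunogenicity against safety. No other is stated in the protocol or SAP, but SAP Section 9 places the complete list in the Data Presentation Plan, which is not available here. The planned listings of adverse events (SAP 7.6.1) and flagged ADA samples (SAP 7.8) would let timing be reconstructed by hand.

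The statement that reactions came mainly with the first infusion has no count behind it. It describes 159 subjects at a 30-Aug-2016 cut-off. The 322-subject update gives no timing and reports Grade 3 or 4 infusion reactions in 4 subjects, so the earlier account is incomplete.

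The strongest point is that a better analysis would have few events. At 18% of 159 there are about 29 reactors. With 20% of them later, that is about 6, of whom about 0.6 would be ADA-positive with no effect, or about 2 with a 5-fold effect (0.5/1.4 = 36%). At 43 of 322 the figures are about 9, 0.9 and 3. Sampling is also coarse after Week 5: the listed weeks are 8, then 4, then 16 weeks apart, so some ADA-positive time would still be classed as negative. These limits stand. They argue for a descriptive presentation, but do not justify crediting first-infusion reactions to later ADA.

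**Conclusion.** The point holds. As specified, the 7.6.5 table mixes reactions before and after ADA and is confounded by time on treatment, so neither a null nor a positive result is interpretable by itself.

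It is tempting to say that the table would give false reassurance. The documents do not support that as the direction of the error: dilution pulls the ratio towards 1, while exposure pushes it above 1 even without an effect. Which dominates is unknown.

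The sizes are illustrations. A 5-fold later risk showing as about 1.3 to 1.9, and a null effect showing as 1.24 to 1.44 (1.01 to 1.26 in the stopping case), rest on assumed first-infusion shares, ADA prevalence, time on treatment and reaction risk. The documents give none of these as numbers. What they do establish is the ever/never definition, counting from first dose, the first-infusion predominance in words, and a first post-baseline sample after that infusion. No primary endpoint or stopping rule depends on this table. The flaw concerns interpretation, not error rates.

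**What to change.** Keep the planned table and add to SAP 7.6.5, for each analyte and as description only:

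- a split of reactions by onset before, versus on or after, the first ADA-positive sample (samples are pre-dose, so a same-day reaction follows its sample);
- reactions after the first infusion, per infusion or per patient-time, in ADA-positive versus ADA-negative time, with each subject contributing negative time until the first positive sample;
- first-infusion reactions shown separately by baseline ADA status, where a baseline sample exists;
- restriction of the treatment-emergent comparison to subjects with at least one post-baseline ADA sample.

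The cost is SAP wording and date logic on adverse event dates and ADA flags already planned for listing, with no new data collection. Baseline ADA needs a check first: as extracted, Table 5.7.3.3-3 (melanoma and SCCHN expansions) marks ADA only at Week 3 and end of treatment, while Protocol 8.3.2.1 lists Week 1. This may be an extraction fault. The downside is small event counts and residual misclassification from the gaps between samples, both of which should be stated with the table.

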7.6.6 Immune-Mediated Adverse Events

The following summary tables will be generated by treatment group and overall. If needed, by patient listing can be provided to support the summary tables.

Summary:

- Summary of related immune-mediated AEs by worst CTC grade (any grade, grade 3-4, grade 5) presented by PT.
- Summary of related immune-mediated AEs by worst CTC grade (any grade, grade 3-4, grade 5) presented by PT for SCCHN participants only.

7.6.7 Multiple Events

Analyses that take into account the multiple occurrences of a given adverse event will be conducted. In order to prepare these analyses, the CRF data will be processed according to standard BMS algorithms²⁶ in order to collapse adverse event records into unique records based on the preferred term. This data will be presented as the rate per 100 patient-years of exposure (observation period). This analysis will take into account all on-treatment events (allowing more than 1 event per subject) and the total duration of exposure. The patient-years exposure will be computed as the sum over the subjects' exposure expressed in years where the duration of exposure is defined as

- Date of last dose of study treatment date of first dose of study treatment + 100+1 days, for subject who are off study treatment and were followed at least 100 days after last dose of study medication. For patients being followed for 150 days, please use 150 days in above calculation.
- Last known date alive- date of first dose of study medication +1, for subjects who are still ontreatment or who are off study treatment and were followed less than 100 days after last dose of study medication.

When specified, the 95% CI of the rate per 100 patient years of exposure will be derived using normal approximation and variance estimation proposed in Cook and Lawless²⁷ (optional). Summary tables will be generated for part 1 and 2 combined.

Summary:

The following summary tables will be provided:

- Summary of frequency of unique adverse events
- Total number and rate (exposure adjusted) of occurrences for all AEs occurring in at least 5% of the subjects treated across treatments.

Listing:

Unique instances of all AEs, i.e., after duplicates have been eliminated and overlapping and contiguous occurrences of the same event (i.e., same PT) have been collapsed.

7.6.8 Clinical Laboratory Evaluations

The results of all protocol-specified clinical laboratory tests, as well as laboratory results outside of the normal range, will be listed. Scheduled laboratory measurements and corresponding change from baseline values will be summarized by treatment and nominal visit for each laboratory test.

The analysis will be based on All Treated Subjects with available laboratory test result ontreatment and up to and including 100 (or 150) days of the last dose of study medication. Laboratory results will be categorized according to NCI CTCAE (version 4) grade.

Summary tables will be generated for Part 1 and 2 combined. Listings will include all available data from Parts 1, 2, 3, and 5.

Summary:

The number (%) of subjects with the following will be summarized by treatment and overall, if appropriate, using the worst CTC grade on-treatment per subject.

- Post-baseline grade
- Grade change from baseline
- Descriptive statistics of laboratory test result and their changes from baseline by treatment and study day

Listing:

A by-subject listing of these laboratory parameters will be provided.

7.6.8.1 Abnormal Thyroid Test

Summary:

Elevated TSH value > ULN and

- with baseline TSH value $\leq ULN$
- with at least one FT3/FT4 test value < LLN within 2-week window after the abnormal TSH test
- with all FT3/FT4 test values \geq LLN within 2-week window after the abnormal TSH test
- with F3/F4 missing within 2-week window after the abnormal TSH test

Low TSH < LLN and

- with baseline TSH value \geq LLN
- with at least one FT3/FT4 test value > ULN within 2-week window after the abnormal TSH test
- with all FT3/FT4 test values \leq ULN within 2-week window after the abnormal TSH test
- with F3/F4 missing within 2-week window after the abnormal TSH test

Listing:

A by participant listing of these specific abnormalities will be provided.

7.6.8.2 Vital Signs and Other Safety Evaluation

Summary:

- Vital signs
- ECG measures

Listing:

- Vital signs
- ECG measures and ECG abnormalities
- Diagnostic procedures
- Medical treatment procedures

7.6.8.3 Physical Examination Findings

All physical examination results (e.g., with abnormal findings) will be listed.

7.7 Pharmacokinetics

Cmax (µg/mL), Tmax (hr), AUC(TAU) (µg.hr/mL), AUC(INF) (µg.hr/mL), CL (L/day), Vss, T-HALF, and Cmin (µg/mL) will be evaluated using non-compartmental analysis in all study subjects by study drug for part 1 and 2 combined. In addition, end of infusion (Ceoinf) and trough (Cmin) concentrations will be calculated at specified visits. Ctough will be listed by doses and visit.

The Pharmacokinetic (PK) population will be used for all listings. Evaluable PK population will be used for summaries and statistical analyses. Analysis will include all evaluable PK data for each analyte (BMS-986015 and BMS-986558).

BMS-986015 PK: All individual PK parameters will be listed for each subject including any exclusions and reasons for exclusion from summaries. Summary statistics will be provided for the following parameters by treatment and study day: Cmax, AUC(TAU), AUC(0-T), AUC(INF), Tmax, Cmin, Ceoinf, CL, Vss and T-HALFeff.

Geometric means and coefficients of variation will be presented for Cmax AUC, Cmin, CL, Vss, and AI_{Cmax}, AI_{AUC}. Median, minimum, and maximum will be presented for Tmax. Means and standard deviations will be provided for THALFeff.

Cmin values will be listed and summarized by treatment and study day, and will be displayed graphically.

Dose proportionality of BMS-986015 PK will be assessed for AUC(INF) after single doses and for Cmax and AUC(TAU) at steady state. The dose proportionality analysis will be conducted for participants from Part 1 and Part 2 only.

To assess the dose proportionality the power model described by Gough et al.²⁸

PK Parameter = A^*Dose^{β}

will be estimated by the simple linear regression of the natural log of the PK Parameter (Cmax, AUC) on the natural log of Dose:

 $E[\log(PK \text{ Parameter})| \text{ Dose}] = \alpha + \beta * \log(\text{Dose}).$

A slope (β) equal to 1 would indicate perfect dose proportionality. For each PK parameters (Cmax, AUC), the point estimates and 90% CI of the slopes will be provided.

Scatter plots or geometric mean plots related to dose proportionality, assessment of steady state or accumulation by dose, vs. study cycle may also be presented.

BMS-986558 PK: All individual PK parameters (Cmin and Ceoinf) will be listed including any exclusions and reasons for exclusion from summaries. Summary statistics will be presented, in terms of geometric means and coefficients of variation for Cmin and Ceoinf.

Results of population PK and exposure-response analyses using sparse or serial PK data for either analyte from this study may be combined with data from other studies and reported separately.

